Secondary outcome measures include adverse effects potentially attributable to antibiotics prescribed for the exacerbation, general health status measured by EuroQoI-5D (EQ-5D),

Costs (total HA cost) and cost-effectiveness, Disease-specific, health-related quality of life over time measured using the CRQ-SAS (dyspnoea, fatigue, emotion function, mastery and total scores).

11. Direct Access to Source Data/ Documents

The investigators and the research assistants in the research team will be responsible for data collection of the project. The investigators will permit trial-related monitoring, audits, IRB review, and regulatory inspection(s), providing direct access to source data and documents.

12. Ethics

The trial will be conducted in accordance with the principles originating in the Declaration of Helsinki, and those in Good Clinical Practice. After patients (or relatives/legal representatives) are assessed as suitable for the Trial, all subjects for this study will be provided a consent form describing this study and providing sufficient information for subjects to make an informed decision about their participation in this study. This consent form is submitted with the protocol for review and approval by the Institutional Review Board (IRB) for the study. The formal consent of a subject, using the IRB-approved consent form, must be obtained before that subject is submitted to any study procedure. This consent form must be signed by the subject or legally acceptable surrogate, and the investigator-designated research professional obtaining the consent. The trial will be conducted in accordance with the information and consent forms.

13. Data Handling and Record Keeping

We will collect baseline and follow up data as appropriate. The principal investigator will be responsible for data safekeeping. We will use a bespoke case report form and an audit trail to ensure that the data captured are consistent, reliable and fully compliant with Good Clinical Practice/regulatory requirements. Information about study subjects will be kept confidential, and managed according to the laws of the Hong Kong Special Administrative Region and, in particular, the Personal Data (Privacy) Ordinance, Cap 486. The name, address or any other identifying information will not be passed on to anyone and data will be assigned an anonymous identification code. The hospital inpatient and specialist clinic outpatient paper medical records are retained for six years and general outpatient paper medical records are kept for three years after the last follow up of a patient. Radiological films are stored only for one to four years. These documents should be retained for a longer period if required.

14. Financing and Insurance

The study would apply for the Health and Medical Research Fund (HMRF).

The study would apply for HKU Master Clinical Trial Insurance Policy.

15. Publication Policy

The research findings will be published in international peer reviewed journals and reports. Individual subjects will not be directly identifiable from the results.

16. References

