5.1 Clinical Question

In adult AECOPD patients in Emergency Departments, does CRP-guided antibiotic treatment, compared with usual care, lead to shorter antibiotic duration without negatively impact on clinical COPD-health status?

5.2 Aims and Hypotheses to be Tested:

This study seeks to establish whether serial CRP level guided clinical judgment can safely and cost-effectively be used to better target antibiotic treatment (include both treatment and discontinuation) for AECOPD in emergency departments to those that are most likely to benefit, so that overall antibiotic exposure duration is decreased without compromising COPD-related health status.

The **primary** objective is to determine whether the addition of a serial CRP levels to usual care for AECOPD leads to shorter antibiotic duration,

The **co-primary objective** is to determine whether the addition of a serial CRP levels to usual care for AECOPD is non-inferior to usual care alone, on COPD health status as measured by CCQ

The **secondary objectives** are the effectiveness of the addition of serial CRP levels to usual care in AECOPD patients on:

- General health status as measured by EQ-5D-5L
- Adverse effects of antibiotics
- Cost-effectiveness of individualised CRP-guided antibiotic treatments.

Primary and secondary objectives and outcome measures are listed in Appendix 5.

We hypothesise that:

- (i) antibiotic duration (defined as 'the number of days of antibiotic treatment') in 28 days among AECOPD patients will be significantly lower for CRP-guided antibiotic treatment (including prescription and discontinuation) than usual care
- (ii) COPD health status as measured by the Clinical COPD Questionnaire (CCQ) has no statistically significant difference between two groups;

- (iii) general health status of AECOPD patients as measured by EQ-5D-5L will not be significantly different between the two groups
- (iv) adverse effects of antibiotic treatment in AECOPD patients will not be significantly different between the two groups
- (v) CRP-guided antibiotic treatment will be more cost-effective than usual care

6. Study design

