6.6.2 Randomization

Patients will be randomized at ED (Day 1). They are randomised in a 1:1 ratio to receive either usual care alone (control), or usual care with addition of CRP trend monitoring for discontinuation of antibiotics. The randomization sequence will be centralised. Computergenerated and randomly permuted blocks allocations will be used. Exacerbation classification suggested by GOLD Initiative is adopted as a minimisation variable so that balance is achieved with respect to differing levels of COPD exacerbation severity.

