6.6.8 Follow Up

The trial team will aim to contact all participants through telephone call, or audio / video call with instant messaging software and application service such as WhatsApp, WeChat, or Instant Messenger, every week after randomization to follow up CCQ and EQ-5D questionnaires. The patient will be met on video call at 4-weeks post randomization. A copy of Chronic Respiratory Disease Questionnaire, self-administered, standardized (CRQ-SAS) and EQ-5D will be sent to patients for completion and return at 6 months.

Week 1 & Week 3

Follow-up call for *week 1 and 3* (±1 working day): The patient will be interviewed for the symptomatology, CCQ and EQ-5D questionnaires.

Week 4

Clinical follow up at *week 4* (±2 working days) by research clinician for medication consumption, adverse effects, sick leave, diagnosis of pneumonia since the initial encounter, any further CRP tests since the initial encounter, health care consultations, CCQ and EQ-5D. The patient will be required to return to the emergency department to undergo fresh sputum collection, throat swab and nasopharyngeal swab anytime during the day of weekdays before end of week 5. The colour of the sputum specimen will be examined. If the patient defaults the follow up at week 4, the team will contact the patient again and collect as many data items as possible. If the patient is unable to present, follow up call will be performed.

Month 6

At *6-months* post randomisation, the trial team member will examine the patient's medical record for any spirometry results, prescription, and healthcare service utilization. The patient will also be sent a copy of CRQ-SAS and EQ-5D then for self-completion. A text reminder message will be sent through with instant messaging software and application service application. Defaulted patients will be called for interview to collect their responses.

7. Assessment of Efficacy

Mean antibiotic duration (in days) within 28-days for AECOPD after randomization.

8. Assessment of Safety

Adverse Event

Events fulfilling the definition of a serious adverse event (SAE), including death, emergency hospitalization for conditions other than AECOPD, life-threatening medical conditions, (required preventive intervention for) disability or permanent damage, or other serious medical events that occur between randomization and 4-week post randomization will be reported to the trial team as soon as it is detected.

9. Statistics and Data Analysis

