Trained physicians and nurses will help with patient recruitment and data collection in the busy emergency departments.

Baseline subject characteristics will be reported using descriptive statistics such as percentage, medians, and interquartile ranges. COPD-related health status, general health status, and duration of antibiotics use will be compared among groups by Fisher exact tests. Adverse effects and number of events in the intervention group compared to control group will be noted and compared by Chi squared tests.

To estimate the between-group difference on primary outcome of antibiotic duration, two sample T test will be used to the analysis. The other continuous variables including the co-primary outcome (CCQ score) and secondary outcome (EQ-5D) will be analyzed in the same manner.

Fisher 's Exact test will be used to make group comparison for categorical variables such as COPD Severity (GOLD grading), COPD exacerbation severity (Anthonisen criteria) and microbiological pathogen. All available data will be summarized descriptively by tables and figures. All analyses will be performed using Stata software (version 16 or updated version) and considered significant at p<0.05.

For missing data handling, multiple imputation methods will be used to assess the sensitivity of primary outcome results to missing data. Assuming at random, generalised linear models will used for the multiple imputations.

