Primary	To determine whether the addition of a serial CRP levels (with advice on interpretation) to usual care for managing AECOPD leads to a reduction in antibiotic exposure for AECOPD without negatively impacting on COPD health status compared to usual care alone.	Recovery in terms of COPD health status as assessed using the Clinical COPD Questionnaire (CCQ) total scores	2 week
Secondary	To evaluate the effect of serial CRP levels for AECOPD in emergency department on:	Prevalence of potentially pathogenic bacteria cultured from sputum at 4 weeks and the proportion of bacteria that are resistant	4-week
		Prevalence of commensal organisms cultured from sputum at 4 weeks and the proportion of bacteria that are resistant	4-week
		Adverse effects potentially attributable to antibiotics prescribed for the exacerbation	Weekly for 4 weeks
		All-cause antibiotic consumption	During the first 4 weeks post randomisation
			week
		orally administered steroids	4-week
		General health status measured by EuroQol-5D (EQ-5D)	Weekly for 4 weeks
		Primary and secondary care consultations, including hospitalisations	4-week & 6-month
		Costs (total HA cost) and cost-	6 month
		Incidence of pneumonia (measured by patient and medical record)	4-week & 6-momnth
		Disease-specific, health-related quality of life over time measured using the CRQ- SAS (dyspnoea, fatigue, emotion function, mastery and total scores)	6-month

Key: AECOPD acute exacerbation of chronic obstructive pulmonary disease, CCQ Clinical COPD Questionnaire, CRP C-reactive protein point-of-care test, CRQ-SAS Chronic Respiratory Disease Questionnaire, self-administered, standardised

Participant Flow Diagram

CONSORT 2010 Flow Diagram

BRONKOTEST

ERS

Evaluation of sputum colour

Sputum purulence correlates with presence of bacteria and favourable effect of antibiotics

european respiratory society every breath counts

Source: https://www.ersnet.org

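### The adverse-effect outcome counts only events attributed to antibiotics for the exacerbation, so misattributed background symptoms can favour the CRP arm even if antibiotics cause no harm

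*Combined protocol and SAP*

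**What the plan says.** Section 5.2 lists "Adverse effects of antibiotics" as a secondary objective. Its hypothesis (iv) is that "adverse effects of antibiotic treatment in AECOPD patients will not be significantly different between the two groups". Section 10 narrows the outcome to "adverse effects potentially attributable to antibiotics prescribed for the exacerbation". The Summary (section 2) does the same, and so does Appendix 5 ("Adverse effects potentially attributable to antibiotics prescribed for the exacerbation"), which sets the assessment weekly for four weeks.

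Section 6.6.8 names adverse effects only at the week 4 contact, which is conducted "by research clinician for medication consumption, adverse effects, sick leave" and other items. Medication use and adverse effects are thus asked about together.

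For the analysis, section 9 says: "Adverse effects and number of events in the intervention group compared to control group will be noted and compared by Chi squared tests". Results are "considered significant at p<0.05". No adjustment for exposure is mentioned. The documents give no event list, causality rule or attribution window, and do not say who makes the attribution.

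**The concern.** In a randomised comparison of adverse effects, whether an event is eligible to be counted should not depend on something the allocation changes. Here it does. The strategy aims to alter both prescription and discontinuation of antibiotics (hypothesis (i), section 5.2). Patients already treated with antibiotics for the exacerbation are excluded (section 6.4.2), so the relevant exposure arises largely after randomisation. Nausea or loose stools in a patient who received antibiotics may be counted; the same symptom in a patient who never had them may not.

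Blinding assessors to arm does not remove this, because judging attribution requires knowing whether antibiotics were taken.

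At stake is a stated secondary objective. An apparent reduction in antibiotic side effects could be reported when total symptoms were equal in the two arms. No other listed outcome is an all-cause comparison of non-serious events that would reveal this.

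**Working it through.** The plan gives no expected rate or power for this outcome, so there is no figure to reproduce. The check asks what the planned comparison would show if antibiotics caused no adverse effects.

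**Inputs from the protocol**
- N = 1,184 (Summary), and "They are randomised in a 1:1 ratio" (section 6.6.2): 1,184 / 2 = 592 per arm.
- Usual-care antibiotic days: mean 9.4, SD 10.3 (background section, local data).
- Mean duration of elevated CRP: 6.4 days, SD 6.8 (same place).
- Antibiotic use in local patients with normal CRP: 96%. Appendix 4, Table 1 reproduces this: (4898 + 318) / 5418 = 96.3%.
- Antibiotic use within 28 days in the cited primary-care CRP trial: 57.0% (CRP) versus 77.4% (usual care).

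**Assumptions, not in the documents**
- Background symptoms unrelated to antibiotics occur in 20% of patients in each arm over 28 days, with onset spread evenly (10% and 30% also tried).
- CRP-arm antibiotic days are 6.4, borrowing the duration of elevated CRP as a proxy.
- The test is two-sided at 0.05.

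**Formulas**
- Events counted only on antibiotic days: p = 0.20 × days / 28.
- Events counted at any time in patients ever given antibiotics: p = 0.20 × share exposed.
- With p̄ the mean of the two proportions, SE = √(2 p̄(1 − p̄)/592) and z = difference / SE. The rejection probability is about Φ(z − 1.96) + Φ(−z − 1.96).

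| Counting rule | Exposure, control vs CRP | Counted, control vs CRP | Risk ratio | z | Rejection |
|---|---|---|---|---|---|
| Antibiotic days only | 9.4 vs 6.4 days | 6.7% vs 4.6% | 0.68 | 0.0214/0.0134 = 1.60 | 36% |
| Antibiotic days only | 9.4 vs 7.4 days | 6.7% vs 5.3% | 0.79 | 0.0143/0.0138 = 1.03 | 18% |
| Antibiotic days only | 9.4 vs 8.4 days | 6.7% vs 6.0% | 0.89 | 0.0071/0.0142 = 0.50 | 8% |
| Antibiotic days plus 7 | 16.4 vs 13.4 days | 11.7% vs 9.6% | 0.82 | 0.0214/0.0179 = 1.20 | 22% |
| Any time, if ever exposed | 77.4% vs 57.0% | 15.5% vs 11.4% | 0.74 | 0.0408/0.0198 = 2.06 | 54% |
| Any time, if ever exposed | 96% vs 80% (assumed) | 19.2% vs 16.0% | 0.83 | 0.0320/0.0221 = 1.45 | 30% |
| Any time, if ever exposed | 96% vs 96% | 19.2% vs 19.2% | 1.00 | 0 | 5% |

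**Sensitivity of the first row**
- Background risk of 10% or 30% gives 20% or 51% rejection, with the same risk ratio.
- In a simulation (constant symptom rate, 20% background, durations varying with the stated SDs and capped at 28 days), the risk ratio is 0.73 and rejection 25%.
- If symptoms cluster early, replace days/28 by 1 − exp(−days/m), with m the mean onset time. For m = 3 days, 19.1% versus 17.6% are counted (ratio 0.92, rejection 10%). For m = 5 days, 16.9% versus 14.4% (ratio 0.85, rejection 22%).

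**After the change.** Counting every event to day 28 regardless of exposure gives a null risk ratio of 1.00. Simulated rejection is 4.7% to 5.5% for background risks of 5% to 50%.

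**The case against.** A reader might infer that the CRP arm must score fewer events because a patient who has stopped antibiotics can no longer contribute one. The documents do not say that. The wording asks only for potential attribution, and Appendix 5 continues assessment to week 4, well past a mean course of 9.4 days. An effect that persists or appears after stopping can be counted. Only patients never given antibiotics for the exacerbation are excluded outright. If nearly everyone in both arms is exposed, as the local 96% suggests is possible, and events count at any time to day 28, the artefact disappears however far antibiotic days differ. This stands, and it makes the bias conditional.

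Nor is 36% an expected error rate. The 6.4 days describes how long CRP stayed raised, not antibiotic use under CRP guidance; the plan states no target difference; and the background rates are assumed.

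An antibiotic-attributed outcome is also legitimate. It matches the stated objective, and fewer real antibiotic harms through less exposure is an intended effect of the strategy. Only misattributed background symptoms are artefact. Hypothesis (iv) expects no difference, so the plan is not framed to claim a benefit.

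Finally, serious events (section 8), pneumonia, consultations and hospitalisations (Appendix 5) are captured without attribution to antibiotics. The case report form is not among the documents, so a standard symptom list may exist. But none of the listed outcomes compares all non-serious events, and a symptom list alone would not help if events were still filtered by attribution before counting.

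**Conclusion.** The concern holds in conditional form. Counting depends on an exposure that the intervention is meant to reduce, and the chi-squared test does not correct for it, so background symptoms can produce an apparent benefit of the CRP arm with no antibiotic toxicity at all. At an assumed 20% background risk, the null risk ratio in the scenarios examined runs from 0.68 to 1.00, and false rejection from the nominal 5% to 54%. Where the trial falls depends on the attribution window, the background rate and timing of symptoms, and the exposure contrast achieved. None of these is stated. The documents do not support saying that the CRP arm is favoured by construction. The point affects a secondary outcome and leaves the co-primary outcomes untouched, but the outcome should be changed, because as written its result turns on an unstated choice.

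**What to change.** At the contacts already planned, ask every randomised patient the same fixed list of symptoms and events. Compare all such events from randomisation to day 28 by arm, in all randomised patients, regardless of antibiotic exposure or attribution. Report the antibiotic-attributed count beside it, with a stated attribution rule and window; it matches the objective and need not be dropped or demoted. Amend section 10, the Summary and Appendix 5, and align section 6.6.8 so that the list is asked at the weekly contacts Appendix 5 implies.

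The cost is outcome wording and one standard question list, with no new visits. The downside is that background symptoms add some noise and slightly dilute a real difference.

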CRQ-SAS: Chronic Respiratory Disease Questionnaire Self-Administered Standardized.

Source: Wijkstra P, TenVergert E, Van Altena R, Otten V, et al. Reliability and validity of the Chronic Respiratory Questionnaire (CRQ). Thorax. 1994; 49(5):465-7.

Appendix 3

EQ-5D-5L

Under each heading, please tick the ONE box that best describes your health TODAY.

MOBILITY

I have no problems in walking about	
I have slight problems in walking about	
I have moderate problems in walking about	
I have severe problems in walking about	
I am unable to walk about	
SELF-CARE	
I have no problems washing or dressing myself	

I have slight problems washing or dressing myself	
I have moderate problems washing or dressing myself	
I have severe problems washing or dressing myself	
I am unable to wash or dress myself	

USUAL ACTIVITIES (e.g. work, study, housework, family or leisure a	activities)
I have no problems doing my usual activities	
I have slight problems doing my usual activities	
I have moderate problems doing my usual activities	
I have severe problems doing my usual activities	
I am unable to do my usual activities	
PAIN / DISCOMFORT	
I have no pain or discomfort	
I have slight pain or discomfort	
I have moderate pain or discomfort	

ANXIETY / DEPRESSION	
I have extreme pain or discomfort	
I have severe pain or discomfort	
I have moderate pain or discomfort	

I am not anxious or depressed	
I am slightly anxious or depressed	
I am moderately anxious or depressed	
I am severely anxious or depressed	
I am extremely anxious or depressed	

Source: HERDMAN, Michael, et al. Development and preliminary testing of the new five-level version of EQ-5D (EQ-5D-5L). Quality of life research, 2011, 20.10: 1727-1736.

Prior work on AECOPD in Hong Kong

Table 1 Outcomes of AECOPD patient

	No Antibiotics		Antibiotics		Antibiotics				
	Not ICU / death	ICU / death	Not ICU / death	ICU / death	Total	p-value	OR (95%CI)		
Normal CRP	200	2	4898	318	5418	0.001	0.15 (0.02, 0.57)		
High CRP	12	0	2422	312	2746	0.382	0 (0, 2.49)		

24 of 27 31st Oct 2021 1.1

Appendix 5

Primary and secondary objectives and outcome measures.

	Objective	Outcome measures	Time point of evaluation (from Randomization)
Primary	To determine whether the addition of a serial CRP levels (with advice on interpretation) to usual care for managing AECOPD leads to a reduction in antibiotic exposure for AECOPD compared to usual care alone.	Antibiotic duration	4 week
Primary	To determine whether the addition of a serial CRP levels (with advice on interpretation) to usual care for managing AECOPD leads to a reduction in antibiotic exposure for AECOPD without negatively impacting on COPD health status compared to usual care alone.	Recovery in terms of COPD health status as assessed using the Clinical COPD Questionnaire (CCQ) total scores	2 week
Secondary	To evaluate the effect of serial CRP levels for AECOPD in emergency department on:	Prevalence of potentially pathogenic bacteria cultured from sputum at 4 weeks and the proportion of bacteria that are resistant	4-week
		Prevalence of commensal organisms cultured from sputum at 4 weeks and the proportion of bacteria that are resistant	4-week
		Adverse effects potentially attributable to antibiotics prescribed for the exacerbation	Weekly for 4 weeks
		All-cause antibiotic consumption	During the first 4 weeks post randomisation
			week
		orally administered steroids	4-week
		General health status measured by EuroQol-5D (EQ-5D)	Weekly for 4 weeks
		Primary and secondary care consultations, including hospitalisations	4-week & 6-month
		Costs (total HA cost) and cost-	6 month
		Incidence of pneumonia (measured by patient and medical record)	4-week & 6-momnth
		Disease-specific, health-related quality of life over time measured using the CRQ- SAS (dyspnoea, fatigue, emotion function, mastery and total scores)	6-month

Key: AECOPD acute exacerbation of chronic obstructive pulmonary disease, CCQ Clinical COPD Questionnaire, CRP C-reactive protein point-of-care test, CRQ-SAS Chronic Respiratory Disease Questionnaire, self-administered, standardised

Participant Flow Diagram

CONSORT 2010 Flow Diagram

BRONKOTEST

ERS

Evaluation of sputum colour

Sputum purulence correlates with presence of bacteria and favourable effect of antibiotics

european respiratory society every breath counts

Source: https://www.ersnet.org

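### Appendix 5 sets antibiotic adverse effects as a weekly outcome, but the follow-up schedule in 6.6.8 names them only at week 4; the two need to be reconciled

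*Combined protocol and SAP*

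**What the plan says.** Section 5.2 lists "Adverse effects of antibiotics" among the secondary objectives, and hypothesis (iv) predicts no significant difference between the arms. Section 9 plans a chi-squared comparison.

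The outcome table in Appendix 5 has a row for "Adverse effects potentially attributable to antibiotics prescribed for the exacerbation", with the time point "Weekly for 4 weeks". The EQ-5D row has the same time point.

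Section 6.6.8 sets out the contacts:

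- In general, participants are contacted "every week after randomization to follow up CCQ and EQ-5D questionnaires".
- At weeks 1 and 3: "The patient will be interviewed for the symptomatology, CCQ and EQ-5D questionnaires".
- Week 2 has no entry of its own.
- At week 4 there is a clinical follow-up "by research clinician for medication consumption, adverse effects, sick leave, diagnosis of pneumonia since the initial encounter", among other items. This is the only contact in 6.6.8 that names adverse effects.

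Section 8 gives serious adverse events between randomisation and week 4 a separate route: they "will be reported to the trial team as soon as it is detected".

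**The concern.** The outcome table calls for four assessments of antibiotic adverse effects and the schedule names one. A research nurse working from 6.6.8 would have no instruction to ask about them at weeks 1, 2 or 3.

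What is at stake is how completely non-serious effects are recorded. A single question at week 4 looks back about four weeks, so some milder events and their timing may be lost. If the loss is similar in both arms, the recorded rates and the difference between them shrink together. That matters because hypothesis (iv) predicts the absence of a significant difference: incomplete recording moves the result towards the prediction. A non-significant chi-squared test would then be hard to interpret.

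Two figures in the protocol's account of the team's prior work in Hong Kong make the look-back relevant. The 2019 admissions had a mean age of 79 years, and AECOPD patients received antibiotics for a mean of 9.4 days (SD 10.3). For many patients, treatment would have ended well before a week-4 question.

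**Working it through.** **Step 1: the passages side by side.** The plan gives no figure to reproduce here; the main check is of the text.

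| Contact | Appendix 5, antibiotic adverse effects | Section 6.6.8, named content |
|---|---|---|
| Week 1 | due | symptomatology, CCQ, EQ-5D |
| Week 2 | due | general weekly contact only (CCQ, EQ-5D) |
| Week 3 | due | symptomatology, CCQ, EQ-5D |
| Week 4 | due | adverse effects named, with CCQ, EQ-5D and other items |

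Contacts at which adverse effects are due under Appendix 5: 4. Contacts at which 6.6.8 names them: 1. The look-back is about 7 days under Appendix 5, and about 4 × 7 = 28 days (±2 working days) if only the week-4 contact asks.

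EQ-5D has the same weekly time point in Appendix 5, and 6.6.8 does carry it in the weekly contacts. One weekly outcome was transferred to the schedule and the other was not, which looks like an omission.

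**Step 2: what missed events could do to the comparison (illustration).** The documents give no adverse-effect rate and no recall rate, so these are assumptions.

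- Patients per arm: 1,184 / 2 = 592, from the Study Summary and the 1:1 allocation, with no loss to follow-up.
- Assumed true rates: p₁ = 15% and p₂ = 10%.
- Assumed share of events missed in both arms: 0%, 20% or 40%.
- Two-sided 5% test of two proportions.

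Recorded rates are the true rate × (1 − share missed):

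- 20% missed: 15% × 0.8 = 12%; 10% × 0.8 = 8%; difference 4 points.
- 40% missed: 15% × 0.6 = 9%; 10% × 0.6 = 6%; difference 3 points.

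Power = Φ[(p₁ − p₂ − 1.96·s₀) / s₁], where s₀ = √[2p̄(1 − p̄)/592], s₁ = √[(p₁(1 − p₁) + p₂(1 − p₂))/592] and p̄ is the mean of the two rates.

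| Recorded rates | s₀ | s₁ | Power |
|---|---|---|---|
| 15% vs 10% (none missed) | 0.01922 | 0.01917 | Φ(0.643) = 74% |
| 12% vs 8% (20% missed) | 0.01744 | 0.01740 | Φ(0.335) = 63% |
| 9% vs 6% (40% missed) | 0.01531 | 0.01528 | Φ(0.000) = 50% |

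Under these assumptions, the loss of power is 74 − 63 = 11 to 74 − 50 = 24 percentage points.

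**The case against.** The strongest reply is that 6.6.8 is not an exhaustive list. Section 10 measures antibiotic duration, the primary outcome, by call at the end of each week, yet 6.6.8 does not mention antibiotic use at weeks 1 and 3 and names medication consumption only at week 4. Section 10 also collects the co-primary CCQ by call at 14 days, while 6.6.8 has no week-2 entry. So absence from 6.6.8 does not prove that an item goes uncollected, and Appendix 5 may be the governing statement. This stands. A reader might infer that the weekly outcome cannot be produced, or that the objective rests on four-week recall. The documents do not support either as a fact: no recall window is stated, and both follow only if 6.6.8 governs.

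Three further points limit the concern:

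- The symptomatology interview at weeks 1 and 3 could pick up some effects. It is not described as adverse-effect collection, however, and 6.6.8 uses a separate term at week 4.
- Serious events are covered by section 8, so the concern is confined to non-serious effects.
- Section 6.6.3 refers to a diagram of data-collection time points that could not be seen for this review. It might show weekly collection. That would settle the intention but would leave 6.6.8 in need of correction.

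On size, a reader might infer that recall alone would leave the comparison underpowered. It would not: the assumed 15% versus 10% has only about 74% power with complete recording. Nor do the documents say when during follow-up most antibiotic adverse effects arise, so the point does not rely on any such claim.

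**Conclusion.** The inconsistency is real: four weekly assessments in Appendix 5 against one named in 6.6.8. It affects a listed secondary objective with its own hypothesis and planned test, but no primary or co-primary outcome. The consequence is conditional. If staff follow 6.6.8 as written, non-serious effects are asked about once, roughly 28 days after randomisation, and the outcome is not the one Appendix 5 defines.

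The power figures show the direction and a plausible order of size only. They rest on assumed rates, equal under-recording in both arms and full follow-up of 592 per arm. The change should be made before recruitment, or as early in it as possible, because early events not asked about at the time cannot be fully recovered later.

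**What to change.** In 6.6.8, add a short antibiotic adverse-effect item to the week 1, 2 and 3 calls, giving week 2 its own entry, and keep the question at week 4. Each contact should ask about the period since the last one. Make sure the case report form and the data-collection diagram agree. The schedule then delivers the Appendix 5 outcome.

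The cost is slightly longer calls; no new contact is needed, since weekly contact is already planned. The alternative is to change the Appendix 5 time point to week 4. That would also reconcile the text and adds no work, but it keeps the longer look-back and the under-recording that may come with it.
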